2.2. Safety Endpoints

1. Incidence of symptomatic intracranial hemorrhage within 24 hours postoperatively: Symptomatic intracranial hemorrhage refers to intracranial hemorrhage (cerebral parenchymal hematoma, subarachnoid hemorrhage, subdural hematoma, ventricular hemorrhage) accompanied by neurological deterioration (NIHSS score increase ≥ 4 points compared to preoperative). Incidence of symptomatic intracranial hemorrhage within 24 hours = Number of subjects in this group with symptomatic intracranial hemorrhage confirmed by CT or MR within 24 hours / Number of subjects in this group undergoing intracranial thrombectomy with a thrombectomy stent $\times 100\%$. CT or MR findings were evaluated by the central reading center.
2. All-cause mortality within 90 days postoperatively: All-cause mortality rate = Number of deaths in this group / Total number of subjects in this group undergoing intracranial thrombectomy with a thrombectomy stent $\times 100\%$.
3. Incidence of SAEs, incidence of AEs.
4. Device defects rate.

3. Analysis Set

Full Analysis Set (FAS): A population defined according to the intention-to-treat principle, comprising all subjects who participated in randomization and received the study product. For patients in whom the primary efficacy endpoint was not observed, missing data will be carried forward using

the Worst Observation Carry Forward (WOCF) strategy.

Protocol-Compliant Set (PPS): Refers to the subgroup of the treated population that completed the trial, excluding those with major protocol deviations (e.g., subjects violating inclusion or exclusion criteria).

Safety Set (SS): Refers to the population of all subjects who used the study device and had at least one safety assessment.

Efficacy analyses will be conducted on the basis of the full analysis set and the per-protocol set. Additionally, all baseline demographic analyses will be performed on the full analysis set, while safety evaluations will be conducted on the safety set.

4. Missing Data Imputation

For patients in the FAS who did not have an observed primary efficacy endpoint, worst-case imputation was applied, defined as failure to achieve immediate reperfusion in the target vessel. No imputation was performed for secondary endpoints or efficacy data in the PPS. Missing safety data were not imputed.

5. Statistical Analysis Methods

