6.1.5.3. Criteria and Procedures for Withdrawal from/Discontinuation of Trial Treatment

The subjects may withdraw from the study at any time during the course of the study without giving a reason: moreover, subjects may choose not to undergo any study procedures after signing the ICF, and if subjects choose not to undergo any study procedures after signing the ICF, the investigator must be informed. However, subjects have the right to continue receiving the standard of care regardless of the cases.

Any subject may also be withdrawn from the study by the investigator based on medical judgement.

Subject's premature discontinuation or withdrawal from the study can be any of the following cases, but not limited to:

- 1) The subject is unwilling to continue participating in this study for any reason;
- 2) For medical or safety reasons, the investigator believes that the subject should be withdrawn from the study;
- 3) Serious protocol violation (confirmed by the principal investigator);
- 4) The investigator or the sponsor requests to terminate the study for any reason;
or
- 5) Death.

For all subjects who terminate the study early, the investigator should make every effort to find out the reasons for withdrawal from the trial, for example: adverse

events, failure of corrective treatment, the investigator's decision or other reasons. The reasons for withdrawal should be recorded in the EDC. Subjects who withdraw early should be requested to complete an early withdrawal visit according to the visit schedule.

Subjects who withdraw from the study will not be replaced, i.e. the randomization number will be uniquely related to each subject and cannot be reused.

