8.1. Expected Drop-out Rate

In determining the sample size, the highest possible drop-out rate during the study is expected to be 10%, including all conditions that make the subjects ultimately excluded from the primary analysis, often referring to major deviation of trial protocol (affecting the primary efficacy evaluation and/or safety evaluation) adjudicated by principal investigator.

It may include the following conditions:

- a) Subjects who, for whatever reason, are unwilling or unable to continue the clinical trial, propose withdrawal from the clinical trial to the investigator and terminate the clinical trial;
- b) Subjects who are lost to follow-up despite not specifically proposing withdrawal from the clinical study but no longer receiving treatment and examination;
- c) Subjects, who experience SAE, should be withdrawn from the clinical study as judged by the investigator;
- d) Subjects, due to poor compliance, fail to complete follow-up for primary outcome;
- e) Lost to follow-up (The investigator cannot reach the subject to return to the

clinic for visit assessment and examination via telephone or mail for two consecutive times).

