8.6. Selection Criteria for Subjects Included in the Analysis and

Justification

Statistical analysis will be carried out on the basis of the following analysis populations. The analysis populations will be clearly defined before the start of statistical analysis. And the analysis populations in this study include:

Full Analysis Set (FAS): The set of subjects determined following the intent-to-treat (ITT) principle refers to the data set constituted by all subjects who participate in the randomized study and receive the investigational product. For patients in whom the primary effectiveness endpoint is not observed, missing data are proposed to be carried forward using the WOCF (Worst Observation Carry Forward).

Per-Protocol Set (PPS): refers to the subgroups of treatment population where the study has been completed with the major protocol violations excluded (which means that the subjects violate the inclusion criteria or exclusion criteria, etc.).

Safety Set (SS): refers to the set of all subjects who receive the investigational device and complete safety evaluation at least once.

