6.1. Subject Distribution

Table1 Case distribution across centers

Center ID	Research Center	Group	Number			
			EnrollmentCount	Dropout Rate (%)	Dropout of ExclusionsRate (%)	Completed
01		Experimental group				
		Control Group				
		Total				
02		Experimental Group				
		Control Group				
		Total				
03		Experimental Group				
		Control Group				
		Total				
.....		Experimental Group				
		Control Group				
		Total				
Total		Experimental Group				
		Control Group				
		Total				

Note 1: Number of completers = Number enrolled - Number of dropouts.

Note 2: Exclusion refers to subjects who completed the trial but were not included in the PPS set.

Table2 Population Distribution by Center

Research Hospital	FAS		PPS		SS		Total
	Center	Experimental group	Control group	Experimental group	Control Group	Experimental group	
01							
02							
03							
.....							
Total							

Table3 Enrolled Cases and Safety/Efficacy Analysis Dataset

Item	Indicator	Experimental Group	Control Group	Total
Reasons for Randomly Assigned				
Early Withdrawal	Completed Trial			
	Adverse events			
	Unsatisfactory treatment response			
	Subject withdrawal of informed consent			
	Protocol violation			
	Other			
	Subject or family member requests withdrawal from the study			
	Loss to follow-up			
	Death			
	Total			
FAS				
PPS				
SS				

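### The per-protocol set requires trial completion, so read literally it drops deaths and later withdrawals whose on-table primary endpoint is already known; this can bias the PPS result, while the FAS is unaffected

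*SAP*

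**What the plan says.** SAP section 3 describes the PPS in these words: "Refers to the subgroup of the treated population that completed the trial, excluding those with major protocol deviations". Protocol 8.6 says that it "refers to the subgroups of treatment population where the study has been completed with the major protocol violations excluded".

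The documents give these indications of what completion means:

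- Protocol 6.1.5.5 runs participation to the final follow-up, at 90 ± 14 days.
- Protocol 6.1.5.3 introduces its list with "Subject's premature discontinuation or withdrawal from the study can be any of the following cases", and item 5 of that list is death.
- SAP Table 3 has a death row among the reasons under "Early Withdrawal".
- SAP Table 1, Note 1 states: "Number of completers = Number enrolled - Number of dropouts". Note 2 uses exclusion for subjects who completed but are not in the PPS, so the PPS sits inside the completers.
- Protocol 8.1 counts loss to follow-up as dropout, and also this case: "Subjects, who experience SAE, should be withdrawn from the clinical study as judged by the investigator".

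The primary endpoint is read on DSA during thrombectomy, and blinded central reading of the procedure images prevails (protocol 6.1.2 and 6.1.6). SAP 5.4.1 bases primary efficacy on FAS and PPS, and Table 24 tests non-inferiority in both. SAP 5.4.2 also runs the secondary endpoints on both. Neither protocol 8.2 nor SAP 5.4.1 says which set decides.

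**The concern.** A programmer who follows the text would remove from the PPS every subject who dies, is withdrawn after an SAE or is lost to follow-up before the 90-day visit. In these subjects the primary endpoint has normally been observed already. The exclusion therefore selects on an event that comes after randomization, treatment and measurement, and it discards valid outcomes.

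In a non-inferiority trial the PPS is the usual check against dilution of a true difference. If deaths are more frequent after failed recanalization, this PPS drops failures selectively and can itself narrow the difference.

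The 90-day mRS is also affected. Without deaths, the PPS comparison of mRS 0-2 is made among survivors only, so a device with more deaths could look as good as its comparator.

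**Working it through.** **Plan's own figure.** With 89% in both arms, a margin of 12.5 points, one-sided 0.025 and 80% power:

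n = (1.960 + 0.842)² × 2 × 0.89 × 0.11 / 0.125² = 98.4, so 99 per arm. Then 99 / 0.90 = 110 per arm, 220 in total. This reproduces the plan and is not in dispute.

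**How many subjects might leave.** The protocol background gives 3-month mortality of 9%-9.6% (hospitalized stroke patients) and 17.9% at 3-6 months (after intravenous thrombolysis). Neither is this population, so they serve only as a range: 220 × 0.09 = 19.8 and 220 × 0.179 = 39.4, or about 20 to 39 deaths. The 10% allowance for all losses is 22.

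**Effect on the primary endpoint.** Let p be the true success rate, ms the 90-day mortality after success and mf the mortality after failure. With deaths removed:

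PPS rate = p(1 - ms) / [p(1 - ms) + (1 - p)(1 - mf)]

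The documents give neither ms nor mf; every value below is an assumption. True rates are set at the margin, 76.5% vs 89%.

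Example with ms = 10%, mf = 30%:
- Test: 0.765 × 0.90 = 0.6885; 0.235 × 0.70 = 0.1645; 0.6885 / 0.8530 = 80.7%.
- Control: 0.89 × 0.90 = 0.8010; 0.11 × 0.70 = 0.0770; 0.8010 / 0.8780 = 91.2%.
- Difference: -10.5 points instead of -12.5.

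The false-pass rates come from 300,000 simulated trials per row, 110 per arm, with an unpooled Wald interval. The FAS passes falsely in about 2.7% to 2.8% throughout.

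| ms / mf | PPS test vs control | Difference | PPS false pass |
|---|---|---|---|
| 8% / 20% | 78.9% vs 90.3% | -11.4 | about 4.5% |
| 10% / 30% | 80.7% vs 91.2% | -10.5 | 6.7% |
| 12% / 45% | 83.9% vs 92.8% | -8.9 | 13.0% |
| 10% / 10% | 76.5% vs 89.0% | -12.5 | 2.8% |
| 20% / 10% | 74.3% vs 87.8% | -13.5 | 1.8% |

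Mortality after failure that differs by arm can move the result either way. With ms = 15%, failure mortality of 20% in test and 40% in control gives -14.4 points; 50% in test and 30% in control gives -6.1. If both devices truly reach 89% and mortality is the same in both arms, the difference stays at 0.

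**Both sets required.** Counting a pass only when FAS and PPS both clear -12.5%, the false-pass rate is 2.2% at 10%/30% and about 2.2% to 2.3% at 12%/45%, no higher than the FAS alone.

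**Effect on 90-day mRS.** If r is the share of an arm with mRS 0-2 and m its mortality, removing deaths turns r into r / (1 - m). As an illustration, if one arm had 9% mortality and the other 17.9%, the divisors are 0.910 and 0.821. Since 0.821 / 0.910 = 0.902, the arm with more deaths could have about 10% fewer good outcomes in relative terms and still show the same PPS rate.

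**Internal conflict.** SAP Table 29 prints an mRS level 6 row (death in protocol Appendix 4) under the PPS columns. If the PPS holds only completers and death is non-completion, that row is always zero.

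**The case against.** *Exclusion of deaths is inferred.* No sentence says that deaths leave the PPS. The drop-out list in protocol 8.1 does not name death, and its item d concerns follow-up for the primary outcome, which a subject who dies after the final angiogram has completed. The level 6 row in Table 29 may show that the authors meant to keep deaths. This stands as a limit on certainty. It does not remove the problem, because the definitions and the table point to different data sets.

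*The direction is not established.* A reader might infer that this PPS must inflate success and make non-inferiority easier to show. The documents do not support that. Protocol 6.1.2 links prognosis to timely opening of the vessel but gives no mortality by recanalization status, and the working shows patterns with no bias or a wider difference. This objection stands in full.

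*The FAS is intact.* It keeps the deaths, counts a missing primary outcome as failure, and is analysed alongside the PPS for both the primary endpoint and the mRS. The higher false-pass rates therefore matter only if the PPS alone, or either set, may decide. This also stands; what remains open is that the plan names no deciding set.

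*The mRS is secondary* and outside the pass/fail criterion in protocol 8.2. That is correct and limits the weight of that part.

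**Conclusion.** The concern holds in a conditional form. The literal PPS definition removes subjects for events that follow an already observed primary endpoint, and it contradicts the SAP's own mRS table. If applied, it would also take every death out of the PPS comparison of 90-day mRS 0-2; that needs no assumption about mortality patterns.

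For the primary endpoint the PPS can be biased toward non-inferiority if failures die more often than successes, similarly in both arms. Over the assumed range of 8%/20% to 12%/45%, the shift is about 1.1 to 3.6 points (from -12.5 to between -11.4 and -8.9). It is zero if mortality is unrelated to recanalization. Nothing here shows that the trial's overall error rate is inflated: the FAS is unaffected, and a requirement that both sets pass would hold false non-inferiority near 2%.

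**What to change.** Before database lock, in SAP section 3 and protocol 8.6:

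1. For the primary endpoint, define the PPS as FAS subjects with no major protocol deviation up to the final angiogram and an available recanalization reading, without requiring 90-day completion.
2. State that later death, SAE withdrawal or loss to follow-up does not remove a subject.
3. For the 90-day mRS, keep deaths in the PPS as mRS 6, which agrees with Table 29.
4. In SAP 5.4.1 and protocol 8.2, state that non-inferiority must be shown in both FAS and PPS, or name the set that decides.

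No new data or patients are needed. PPS success rates may come out slightly lower. The change must be recorded: protocol 8.5 says that analysis sets should in principle not be modified, and an edit to protocol 8.6 is an amendment needing ethics approval (protocol 12.1 and 14). Made after results are known, it would look driven by them.

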5.1. General Principles

Statistical analyses were performed using SAS version 9.4 statistical software.

Descriptive Statistics: Count data were described using frequency and proportion; continuous data were described using mean, standard deviation, maximum, minimum, median, and 25th and 75th percentiles.

Statistical Inference: For comparisons between two groups, quantitative indicators were analyzed using paired t-tests or Wilcoxon signed-rank tests based on data distribution. Categorical indicators were analyzed using chi-square tests or exact probability methods (if chi-square tests were not applicable). Ordinal data were analyzed using Wilcoxon signed-rank tests or the Cumulative

Hypothesis Test (CMH).

Unless otherwise specified, all statistical tests were two-tailed. A P-value < 0.05 (two-tailed) was considered statistically significant.

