Evaluation method: The recanalization time will be judged by intraoperative procedure and the vascular condition shown by imaging.

Formula: Recanalization time = Recanalization success time - Femoral artery puncture time

Precautions: The recanalization time is the time from the completion of femoral

artery puncture to recanalization success. If the vessel is not revascularized, the end time point is recorded as the time point at the end of operation. Criterion for instant recanalization success: target vessel recanalization with mTICI grade of 2b or 3 after thrombectomy with the investigational device. The investigator's judgment intraoperatively shall prevail.

- **Proportion of subjects with NIHSS score decrease > 4**

Recording time and method: The preoperative and postoperative NIHSS scores are compared by three time points: pre-operation, 24 ± 12 h postoperatively and 7 ± 2 d postoperatively (before discharge in case of premature discharge) to analyze the degree of impairment and improvement of neurological functions preoperatively and postoperatively. The NIHSS score is the total score based on NIHSS scale (as shown in Appendix 5).

Proportion of subjects with NIHSS score decrease > 4 = Number of subjects with NIHSS score decrease > 4 postoperatively in this group/Number of subjects treated with thrombectomy through stents in this group $\times 100\%$.

- **Success rate of device operation**

Definition: The success rate of device operation is the proportion of device operation success. Device operation success is defined as successful delivery of the investigational device to the diseased vessel site to complete accurate deployment and withdrawal.

Evaluation time: Intraoperatively (evaluation endpoint)

Evaluation site: target vessel

Evaluation method: The success rate of device operation is calculated by intraoperative evaluation of whether the delivery, deployment and withdrawal of the thrombectomy device are completed.

Formula: Device operation success = Number of devices delivered, deployed and withdrawn/Number of all investigational devices used in this group $\times 100\%$.

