7.1.2. Statistical Analysis Methods

7.1.2.1. General Principles

Statistical description: The categorical data are described as frequency and proportion; while the continuous data are described as mean, standard deviation, maximum, minimum, median, 25th quantile, and 75th quantile.

Statistical inference: For the comparison of general situation of the two groups, the quantitative indicators between groups are compared using group t test or Wilcoxon rank sum test according to the data distribution, classification indicators using chi-square test or accurate probability method (if the chi-square test is not applicable), and ordinal data using Wilcoxon rank sum test or CMH test.

All statistical tests, if not specified, are two-sided and the difference is considered statistically significant when P value is <0.05 (two-sided). In addition to the statistical methods listed below, detailed and additional exploratory analyses may be required and confirmed in the Study Reports and Statistical Analysis Plan (SAP).

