7.2. Calculation of Sample Size

7.2.1. Total Sample Size

The primary endpoint of the study is the success rate of recanalization, using non-inferiority test. A total of 220 patients are planned to be enrolled and randomly assigned to the test or control group in a 1:1 ratio, with 110 subjects in each group. mTICI can reach 76% at 6-16h according to DEFUSE-3 and 84% at 6-24h according to DAWN. Within 6 h, mTICI is 86% in EXTEND-IA, 88% in SWIFT PRIME, and 87% in PISTE.

According to the estimation combined with the existing clinical evidence and the experience of clinical experts, assuming that the recanalization success rate after treatment is 89% in both the test group and control group within 24h ^[10-19], the non-inferiority margin is set at 12.5% after discussion between the clinical investigator and the sponsor. When the significance level α of statistical test is set as one-sided 0.025 and the power $1-\beta$ is set as 80%, the sample size is calculated as 99 in each group. In consideration of the maximum possible dropout rate of 10% in the study, the sample size in each group is 110. Therefore, 220 subjects are required in total. It is calculated according to statistical principles that,

the corresponding sample size formula is:

$$n_T = n_C = \frac{(Z_{1-\alpha/2} + Z_{1-\beta})^2 [P_C(1 - P_C) + P_T(1 - P_T)]}{(|D| - \Delta)^2}$$

where, n_T and n_C are the respective sample size of the test group and control group; $Z_{1-\alpha/2}$ and $Z_{1-\beta}$ are the percentiles in standard normal distribution; P_T is the expected success rate of recanalization in the test group, P_C is the expected success rate of recanalization in the control group; $|D|$ is the absolute value of the

difference between groups in the expected recanalization, $|D| = |P_T - P_C|$; Δ is the non-inferiority margin (taking the negative value).

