2.1.2. Secondary efficacy endpoints

1. 90-day Postoperative mRS 0-2 Score Ratio: $\text{mRS 0-2 Score Ratio} = \text{Number of subjects with mRS 0-2 score at 90 days postoperatively} / \text{Number of subjects undergoing thrombectomy via intracranial thrombectomy device} \times 100\%$.
2. Time to recanalization: $\text{Time to recanalization} = \text{End time} - \text{Femoral artery puncture time}$ (If recanalization is successful, the end time is the time of successful recanalization; if no recanalization occurs, the end time is recorded as the time of procedure completion). Here, recanalization refers to successful target vessel recanalization with mTICI grade 2b or 3 following thrombectomy using the investigational device.
3. Postoperative NIHSS score improvement >4 points: Improvement in NIHSS score at 24 ± 12 hours postoperatively, 7 ± 2 days postoperatively/prior to discharge compared to baseline. $\text{Percentage of subjects with } >4\text{-point NIHSS improvement} = \text{Number of subjects in this group}$

with >4-point postoperative NIHSS improvement / Number of subjects in this group treated with thrombectomy via thrombotic stents $\times 100\%$.

4. Success rate of device operation: Defined as successful delivery of the device to the target lesion site, followed by accurate deployment and retrieval. Success rate of device operation = Number of devices successfully delivered, deployed, and retrieved in this group / Total number of devices used in this group $\times 100\%$.

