5.4.2. Secondary Endpoints

Secondary efficacy assessments were based on the full analysis set (FAS) and the per-protocol set (PPS).

The 90-day postoperative mRS 0-2 rate, the proportion of subjects with NIHSS improvement >4 points, and the device procedural success rate were analyzed as categorical data; recanalization time was analyzed as a quantitative endpoint.

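### SAP 5.1 names paired tests for comparing two independently randomised arms, where the protocol names unpaired tests

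*SAP*

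**What the plan says.** **Tests.** SAP 5.1, on comparisons between two groups: "quantitative indicators were analyzed using paired t-tests or Wilcoxon signed-rank tests based on data distribution". For ordinal data it names the signed-rank test or CMH. Protocol 7.1.2.1, on the same comparisons: "the quantitative indicators between groups are compared using group t test or Wilcoxon rank sum test according to the data distribution". For ordinal data it names the rank-sum test or CMH.

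**Design.** Protocol 7.2.1: subjects are "randomly assigned to the test or control group in a 1:1 ratio, with 110 subjects in each group". Neither document defines matching, crossover or any other pairing.

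**Recanalisation time.** SAP 5.4.2 says only that "recanalization time was analyzed as a quantitative endpoint", so the SAP 5.1 default applies. For failures, SAP 2.1.2 says that "if no recanalization occurs, the end time is recorded as the time of procedure completion". Protocol 6.1.6 has the same rule: "If the vessel is not revascularized, the end time point is recorded as the time point at the end of operation".

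**Primary endpoint.** SAP 5.4.1 uses the 95% CI of the rate difference and a centre-adjusted CMH analysis. SAP 5.1's paired tests do not enter it.

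**The concern.** A paired test analyses within-pair differences. Subjects in separate randomised arms form no pairs, so the SAP instruction has no defined meaning. A programmer must depart from it or invent a pairing, for example by row order. The first is an undocumented change to a pre-specified method. The second makes the p-value depend on how the file was sorted.

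The rule reaches every quantitative between-group row with a p-value: recanalisation time (Table 30), the NIHSS scores supporting the responder endpoint (Table 31), and baseline and procedural rows such as age, vital signs, ASPECTS and number of passes (Tables 4, 9, 12, 21). Table 22 counts devices, so pairing has even less meaning there. Ordinal rows not labelled CMH, such as the 90-day mRS grades in Table 29, fall under the signed-rank wording.

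A lesser matter concerns the same endpoint. Because failures are timed to the end of the procedure, the comparison mixes how fast the device works with how long the operator continues.

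**Working it through.** **1. The plan's own figure.** Inputs from protocol 7.2.1: success 89% in both arms, margin 12.5 points, α "set as one-sided 0.025 and the power" 80%.

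n = (1.960 + 0.842)² × [0.89×0.11 + 0.89×0.11] / 0.125² = 98.36, rounded up to 99. Then 99/0.9 = 110 per arm, 220 in total. This agrees with the protocol ("is set as 80%, the sample size is calculated as 99 in each group"). The endpoint is binary, so correcting SAP 5.1 leaves these figures unchanged.

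**2. The texts side by side.**

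| Data | Protocol 7.1.2.1 | SAP 5.1 |
|---|---|---|
| Quantitative | group (two-sample) t or rank-sum | paired t or signed-rank |
| Ordinal | rank-sum or CMH | signed-rank or CMH |

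Both sentences concern comparison of the two groups, so within-patient change cannot be what SAP 5.1 means.

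**3. Unequal arms.** The FAS requires receipt of the product, so equal arms cannot be assumed. With 105 v 99 subjects, for example, a paired test has to drop 105 − 99 = 6.

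**4. Error rate and power with forced pairing.** The documents give no procedure times. Assumed: log-normal times, median 60 min for successes and failures, log-SD 0.5, 89% success, 3,000 simulated trials per setting, two-sided 5%.

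| Setting | two-sample t | rank-sum | paired t | signed-rank |
|---|---|---|---|---|
| No difference, 110 v 110 | 5.3% | 5.2% | 5.4% | 5.4% |
| No difference, 105 v 99 (paired tests on 99) | 5.5% | 4.9% | 5.5% | 5.4% |
| Success times 20% shorter in one arm, 110 v 110 | 75.6% | 81.1% | 75.3% | 77.8% |

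The Monte Carlo standard error at 5% is √(0.05×0.95/3000) ≈ 0.4 points. Type I error is not inflated, and the power loss is at most about 3 points.

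**5. Dependence on the pairing.** One simulated data set, 110 per arm, medians 52.2 (60 × 0.87) and 60 min, log-SD 0.5. Rank-sum p = 0.30; two-sample t p = 0.31. Over 2,000 random pairings of the same data:
- signed-rank p ran from 0.048 to 0.81, with the central 95% between 0.14 and 0.52; one pairing (0.0005 × 2,000) fell below 0.05
- paired t p ran from 0.23 to 0.37

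**6. Timing of failures (secondary).** With success times alike in both arms, the rule shifts the difference in means by

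(difference in failure rate) × (mean stop time in failures − mean time in successes).

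Take success of 76.5% v 89%, a failure-rate difference of 0.235 − 0.11 = 0.125. The success median is 60 min in both arms and log-SD 0.5, so each mean is its median × e^0.125 = 1.133. The shift is 0.125 × (m − 60) × 1.133, where m is the assumed median stop time in failures. The rejection rates are from simulation (rank-sum, two-sided 5%).

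| m (min) | Shift for the arm that fails more | All significant results | Of which favour that arm |
|---|---|---|---|
| 30 | −4.2 min (looks faster) | 19.0% | 18.9% |
| 60 | 0 | 5.2% | 2.4% |
| 90 | +4.2 min (looks slower) | 9.6% | 0.2% |
| 120 | +8.5 min (looks slower) | 18.1% | under 0.1% |

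The sign turns on m, which the documents do not give.

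**The case against.** The strongest reply is that this is a drafting or translation slip. The same SAP paragraph expands CMH wrongly, and the protocol already has the right tests. Protocol 8.5 says that the main methods should in principle not be modified, and a paired procedure on unequal arms would probably be noticed at programming. All of this is plausible, though the documents cannot settle it. It lowers the likely harm, but the SAP is the operative instruction and still names the wrong tests.

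A reader might infer that the recanalisation-time result would be invalid in the sense of producing excess false positives. That is not supported: with arbitrary pairing the rejection rate under no difference stays near 5%. Nor is there a threat to the trial's conclusion. The primary analysis (SAP 5.4.1) and the pass/fail rule (protocol 8.2) do not use these tests, and mRS 0-2 and the NIHSS responder proportion are analysed as categorical (SAP 5.4.2).

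A reader might also infer that timing failures to the end of the procedure favours the arm that fails more. That holds only if failed procedures end sooner than successful ones. Protocol 6.2.1.3 allows other measures after failure, which makes later endings plausible, and the rule would then count against that arm. The rule is also disclosed in the endpoint's own name and is the same in both documents. It is a debatable definition, not an error. What remains is that Table 30 as laid out does not let a reader separate successes from failures.

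**Conclusion.** SAP 5.1 is wrong as written and contradicts protocol 7.1.2.1. Its paired tests are inapplicable to this design, and any p-value obtained by forcing them depends on an arbitrary pairing. The consequence is limited to recanalisation time, the supporting score rows, and quantitative or ordinal baseline and procedural rows. The correction should be made before analysis because it is an operative rule and costs nothing; the design itself is not at risk.

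The contradiction and the absence of pairs rest on the text alone. The simulated sizes rest on assumed log-normal times. The range of 0.048 to 0.81 comes from one data set and is its extreme spread, so it illustrates dependence on pairing and does not estimate how often a conclusion would change.

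The failure-timing matter is secondary, its direction is undetermined, and it calls for fuller reporting, not a new definition.

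**What to change.** **Required.** In SAP 5.1, for quantitative data, replace the paired t-test with the two-sample t-test and the Wilcoxon signed-rank test with the Wilcoxon rank-sum test. For ordinal data, replace signed-rank with rank-sum and keep CMH. This restores protocol 7.1.2.1. The cost is a wording change, recorded as protocol 8.5 requires; no subjects, data or sample-size work are needed.

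**Optional.** Keep the protocol's definition of recanalisation time. Add to Table 30:
- the number of failures in each arm
- the time among successes, by arm
- a sensitivity rank-sum analysis with failures tied at the worst rank

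The cost is a few table rows and lines of code. The worst-rank analysis partly restates the primary endpoint, so it should be a sensitivity analysis and not a replacement.
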